	
Phase 0 – Pre-Cooling Monitoring (30 minutes): Manual temperature (core and tympanic), ICP (when available) and blood pressure data collection every 5 minutes (and some additional observations, see above).
 
Phase 1 – Cooling Treatment: Manual data collection will occur at a minimum:
 
• 5 minute intervals for first 30 minutes of cooling period.• 30 minute intervals for first 8-hour cooling period.• 2 hour intervals for remaining 16 hour of cooling (if applicable). 
Phase 2 – Short-Term Post-Cooling Monitoring: Manual data collection will occur at 15 minute intervals during this 2-hour period immediately following COOLSTAT cooling.
 
Phase 3 – Long-Term Post-Cooling Monitoring: Manual data collection will occur at minimum four hour intervals through this 22-hour post-COOLSTAT cooling period.
 
Any additional data collections and the reasons for them shall be documented in the study case form.

Study Population	70 adult febrile patients in the neurosciences intensive care unit, with ischemic or hemorrhagic stroke, seizure, or metabolic encephalopathy. Hemorrhagic stroke includes both intracerebral hemorrhage and subarachnoid hemorrhage stroke. Only the first 30 subjects who meet post-consent eligibility criteria will receive COOLSTAT therapy.
Regimen	COOLSTAT® Transnasal Thermal Regulating Device will be applied to patients at a pressure not to exceed 30 cm H ₂ O (as automatically regulated by the device). A closed-loop control system in the COOLSTAT will modulate and control air flow and maintain the subject's core temperature between 36 °C and 37.5 °C, as measured by a hospital supplied embedded temperature sensor (esophageal, bladder, or 3M™ SpotOn™ temperature sensor). The device will be set to target of 36.5 °C.

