3.2 Control System

The COOLSTAT device can be operated in either an open loop cooling mode or a closed-loop cooling mode. In the open loop mode, the air flow of the device is set by the operator over a range of 5 flow settings (from low to high), limited by the max pressure supply of the device to ensure safety (discuss herein). The energy removed by the device is expected to be proportional to the air flow setting and the duration of time used. In the closed-loop control mode, the device's control system is designed to lower the subject's temperature as quickly as practical using a high flow rate of air provided by the blower. As the patient's temperature approaches a pre-set target temperature (as selected by the operating clinician), the air flow of the device is automatically reduced, at which point the blower driver controls to a target patient temperature by adjusting the flow rate. The blower will use PID control (proportional-integral-derivative) to cool the patient to the target temperature by adjusting the flow rate between approximately 0 and 60 LPM.

This study will use the closed-loop control setting only. The COOLSTAT receives temperature feedback from an esophageal, bladder, or 3M SpotOn™ temperature sensor, all of which are standard sensors used at the study sites with other hospital devices. The selection of which sensor will be at the discretion of clinical staff, following existing

protocols. The SpotOn is currently used as a first line sensor since it has been validated by the University of Maryland Medical Center as providing a quality core temperature reading and is non-invasive. While patient interventions, such as a bolus of cold liquid briefly flowing over an esophageal temperature probe, may temporarily alter the probe's reading from the true core temperature, such events are brief and will not affect COOLSTAT function. The COOLSTAT control system prevents the machine from a rapid or exaggerated response to a brief change in core temperature input. Bladder temperature sensors are used less frequently, but are considered an acceptable core temperature sensor in the event that a subject is unable to have a SpotOn or esophageal temperature probe. The COOLSTAT has a display that shows both the patient's current temperature (from the core temperature sensor) and the target temperature. The integrity of the control system to control and maintain the subject's temperature will be closely monitored in this study.

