2. **Device and Disposable Set-Up Risks:** Device and disposable set-up risks will be mitigated by proper training of study staff who may interact with the device. The COOLSTAT has been evaluated for ease of use by preclinical study staff (independent of company and unfamiliar with device prior to the study). Device set-up and disposable use was generally found to be intuitive. The COOLSTAT hardware includes features like a unique connector for the nasal mask attachment that mitigate the risk of improper device use.

There are two potential risks for disposable misuse during COOLSTAT treatment: 1) desiccant cartridges may be used longer than suggested and allowed to reach room/supplied air humidity level, and 2) failure to replace the saline bag providing the "spritz" delivery. Although there are built-in device warning messages and alarms, desiccant cartridges may not be changed out in a timely manner as air supplied to the subject becomes more humid (and therefore less effective at drying air). The result would be less effective evaporative cooling due to less dry air being delivered. However, the blower would begin to deliver higher air flow (up to the pressure limit) to compensate for any decreased effectiveness (which would be registered by an increase in core temperature). Testing in hospital conditions (using wall air port as air source) has demonstrated an effective operating period for the desiccant cartridge from 2-3 hours on the low end, and up to 5-6 hours on the high end, which is likely a sufficient time to cool the subject to normothermia. If the desiccant cartridge is not changed when indicated, cooling to the subject will likely be reduced and the subject's temperature could begin to rise. This will be detected by temperature alarms, as well as clinical and study personnel monitoring the subject.

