13.0 Statistical Analysis Plan

The primary efficacy analysis for cooling performance will be based on the evaluable populations of subjects who undergo cooling treatment with the COOLSTAT System. Analysis will be performed on treatment initiated and treatment completed populations. Subjects who achieve normothermia (core temperature $\leq 37.5^{\circ}\text{C}$) within 4 hours of starting COOLSTAT treatment and maintain normothermia for the duration of the treatment will be determined to have been treated successfully.

The primary efficacy analysis for temperature maintenance will be based on the evaluable population of subjects who maintain normothermia (core temperature between 36°C and 37.5°C) for at least 80% of the time following the initial achievement of 37°C will be determined to have been treated successfully.

The proportion of subjects fulfilling success criteria and 90% confidence intervals will be reported and compared to the a priori minimum acceptable criteria:

- at least 75% of the subjects will reach normothermia (core temperature $\leq 37.5^{\circ}\text{C}$) within 4 hours of starting COOLSTAT cooling, and
- at least 75% of the subjects' core temperatures remain between 36°C and 37.5°C for 80% of the steady state time following the initial achievement of 37.5°C .

Continuous measurements will be summarized using the mean and standard deviation. Categorical variables will be reported using percentages and confidence intervals. Data collected will be plotted to demonstrate the change in core temperature from baseline.

An exploratory analysis of participant subgroups will be performed, stratified by stroke presentation (ischemic versus hemorrhagic). Cooling performance and AEs will be evaluated by subgroup.

Double nostril air flow and single nostril air flow subjects will not be merged or directly compared. The results from subjects treated with single nostril flow will be analyzed separately from subjects treated with double nostril air flow.

Subjects 1 through 20 will be assigned to the double nostril air flow treatment group:

- Subjects 1 through 10 will be treated for 8 hours (N=10)
- Subjects 11 through 20 will be treated for 24 hours (N=10)

Subjects 21 through 30 will be assigned to the single nostril air flow treatment group

- Subjects 21 through 30 will be treated for 24 hours (N=10).
- Subjects 21 through 30 will be treated using a dose escalation model:
 - Dosing for this cohort (flow rate) will begin at 30 LPM.

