 - The dose will be increased by 10 LPM if 3 consecutive subjects complete the study protocol with no serious adverse events (as listed in section 10.5) or unanticipated adverse device events.
 - Up to three doses will be evaluated in this cohort (30 LPM, 40 LPM, 50 LPM).
- The purpose of this cohort is to assess the safety of and optimal dose for the single nostril air flow configuration of the CoolStat.
- Each subject will be examined for adverse events, serious adverse events, and unanticipated adverse device events by an intensivist or otolaryngologist within 24 hours of completing CoolStat therapy.
- Each flow rate cohort must be evaluated by an intensivist or otolaryngologist prior to advancing the protocol to the next increased flow rate cohort.

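### In the single-nostril cohort (subjects 21-30) a flow level can be cleared without checking that its flow was delivered, and the escalation rule cannot identify an optimal dose

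*Combined protocol and SAP*

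**What the plan says.** **Dose and purpose (section 13.0).** Subjects 21-30 form a 24-hour single-nostril cohort, analysed apart from the double-nostril subjects. The assigned dose is a flow rate: "Dosing for this cohort (flow rate) will begin at 30 LPM". Up to three levels are planned: 30, 40 and 50 LPM. The aim is given as: "The purpose of this cohort is to assess the safety of and optimal dose for the single nostril air flow configuration of the CoolStat".

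**Escalation (section 13.0).** "The dose will be increased by 10 LPM if 3 consecutive subjects complete the study protocol with no serious adverse events"; the sentence goes on to add unanticipated adverse device events. There is also a clinical step: "Each flow rate cohort must be evaluated by an intensivist or otolaryngologist prior to advancing the protocol to the next increased flow rate cohort".

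**Control mode.** Section 3.2 states: "This study will use the closed-loop control setting only". In that mode the controller works by "adjusting the flow rate between approximately 0 and 60 LPM" and reduces flow as the subject approaches the set temperature. Operator-set flow is described only for the open-loop mode, which the study does not use. Section 1.0 ("A closed-loop control system in the COOLSTAT will modulate and control air flow") and section 9.3 repeat closed-loop operation without an exception for this cohort.

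**Data available.** Section 12.6 has the device record flow every second, with transfer to cloud storage that the sponsor and monitor can review.

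**The concern.** A dose-escalation record is informative only if subjects at a level received that level. Here the assigned number and the control mode are described in separate places and never joined. The text does not say whether 30, 40 or 50 LPM is a fixed flow, an average or a ceiling, and no step before escalation asks what flow was delivered. Three subjects could therefore clear 40 LPM after spending little time near 40 LPM, and the move to 50 LPM would rest on a safety record that belongs to lower flows.

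The second issue is the aim. An optimal dose needs a criterion that weighs cooling against harm, and enough data to tell the levels apart. The rule responds only to adverse events. Section 13.0 gives no cooling criterion by level, no selection rule and no instruction to report by level. The last level cleared could then be taken as optimal when the rule has shown only that three subjects had no qualifying event.

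**Working it through.** **Plan's own figure.** The plan gives no calculation for this cohort. Its one sample-size figure (section 6.6) reproduces: [(1.28·√(0.9·0.1) + 0.84·√(0.75·0.25))/0.15]² = 24.85, rounded up to 25. It concerns the study as a whole and has no bearing on the comparison of three flow levels.

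**Step 1: can a level be cleared on little exposure at its flow?** Setting the sections side by side:

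- Sections 3.2 and 5.1.1: flow is high at first and falls once the subject nears or reaches target. A subject who responds early may spend most of the 24 hours below the assigned level.
- Section 9.3: a subject not normothermic at 4 hours is normally taken off the device, though the investigator may continue. Section 14.3 keeps such subjects in data collection to completion. The SAP does not define completing the protocol, so a subject with about 4 of 24 hours on the device (4/24 = 17%) could arguably count towards the three.
- Section 10.4 lists insufficient cooling as an anticipated event, so poor cooling alone need not block escalation.
- Section 1.0: delivery pressure may not exceed 30 cmH2O. The documents give no single-nostril pressure-flow data, so whether 50 LPM can be reached within that limit is unknown.
- Section 13.0: the two conditions for escalation are event-free completion by three consecutive subjects and an evaluation by an intensivist or otolaryngologist. Neither mentions delivered flow.

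So the rule permits clearance on little exposure. How often that would happen cannot be computed, because the documents give no hours at a given flow.

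**Step 2: subjects per level.** With 10 subjects and three needed per step, the split is 3, 3 and 10 − 6 = 4 if each level clears on its first three subjects. Any qualifying event leaves fewer for the higher levels.

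**Step 3: what those numbers say about cooling.** Exact (Clopper-Pearson) two-sided 90% intervals for the proportion successfully cooled, at the confidence level that section 13.0 uses:

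| Result | Lower limit | Upper limit |
|---|---|---|
| 3/3 | 0.05^(1/3) = 36.8% | 100% |
| 2/3 | 13.5% (solves 3p² − 2p³ = 0.05) | 0.95^(1/3) = 98.3% |
| 4/4 | 0.05^(1/4) = 47.3% | 100% |

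The intervals overlap almost entirely.

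**Step 4: would the best level look best?** As an illustration only, assume true success rates of 60%, 75% and 90% at 30, 40 and 50 LPM, with independent subjects. Summing the binomial probabilities over 3, 3 and 4 subjects, the 50 LPM level has the strictly highest observed proportion with probability 0.43 and ties for highest with probability 0.36. In the remaining 1 − 0.43 − 0.36 = 0.21 a lower level looks better. This is a large assumed difference, and the cohort still ranks it correctly without a tie less than half the time.

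**The case against.** The strongest reply is that section 13.0 already settles the dose. Flow rate is the dose, it starts at 30 LPM and it rises only when the condition is met. Section 14.15 does not allow deviations. The cohort text was added in revision D and is more specific than the general device description in section 3.2. Set-up is left to the Operator's Manual, which was not available and may set a limit. This largely stands. A reader might infer that a subject assigned 30 LPM could be driven to 60 LPM, twice the level, when cooling lags, and might cite section 5.1.1: "the blower would begin to deliver higher air flow (up to the pressure limit) to compensate for any decreased effectiveness". The documents do not support that. The sentence concerns late desiccant changes in a general risk section, and 0-60 LPM is the range of the control system, not dosing for this cohort. What is missing is a sentence saying how the limit applies.

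Other replies have partial force:

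- Subjects must complete the protocol, which arguably includes receiving the assigned flow. That reading is available but not written, and section 14.3 allows a looser one.
- Subjects start at 38.3 °C or more against a 36.5 °C target, a gap of at least 1.8 °C, and the device begins at high flow. Reaching the level briefly is therefore likely, but time spent at it remains open.
- The log would reveal under-delivery. It would, but no rule requires anyone to look before escalating.
- The study is exploratory, the DSMB meets after any serious adverse event, and three clean subjects are weak safety evidence in any three-per-level scheme. All true, which is why no larger cohort is asked for.
- Section 1.0 plans to examine cooling response against air flow rate. That is to confirm cooling models and the control algorithm; it defines no optimum.

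**Conclusion.** The point holds in two parts. First, escalation does not require evidence that the assigned flow was delivered, so the safety record of a level may describe lower flows. This follows from the text alone; its frequency cannot be estimated from the documents. Second, an adverse-event-only rule with 3, 3 and 4 subjects cannot support an optimal-dose conclusion. The exact 90% intervals for cooling success run from 36.8% to 100% for 3/3 and from 13.5% to 98.3% for 2/3, assuming that each level clears at once.

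The missing statement that 30, 40 and 50 LPM are maxima is a clarification. It is not evidence that subjects would be exposed above their level, because section 13.0 makes the level the dose and the Operator's Manual may enforce it. The change should be made before subject 21 is treated, because it affects what the cohort can conclude.

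**What to change.** 1. **Check delivered flow before each escalation.** From the section 12.6 log, review peak flow, mean flow and hours at the assigned level for each subject, alongside the clinical evaluation. Do not count a level as cleared on subjects who did not reach it, and say whether a subject removed at 4 hours counts as completing.
2. **Report safety and cooling by assigned level.** Show delivered flow as descriptive exposure only. Under closed loop it depends on the subject's own temperature response, so slow responders receive more flow and a comparison by delivered flow would be confounded.
3. **Replace the optimal-dose aim** in section 13.0 with a descriptive tolerability aim for the levels studied.
4. **As a clarification,** state in sections 3.2, 9.3 and 13.0 that 30, 40 and 50 LPM are the maximum closed-loop flows for subjects 21-30.

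The cost is amendment wording, a short log check before each escalation, one table from data already recorded, and the loss of the optimal-dose claim. No extra subjects are needed.

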13.1 Primary Performance Outcome Analysis

The primary hypothesis regarding cooling performance is that at least 75% of the subjects will reach normothermia (core temperature $\leq 37.5^{\circ}\text{C}$) within 4 hours of starting COOLSTAT cooling.

The primary hypothesis regarding temperature maintenance is that at least 75% of the subjects' core temperatures remain between 36 °C and 37.5 °C for 80% of the steady state time following the initial achievement of 37.5 C.

13.2 Secondary Performance Outcome Analysis

To analyze the COOLSTAT's impact on the shivering response, the incidence of anti-shivering actions will be assessed.

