Hypothesis	
The primary hypothesis regarding cooling performance is that at least 75% of the subjects will reach normothermia (core temperature $\leq 37.5^{\circ}\text{C}$) within 4 hours of starting COOLSTAT cooling.
 
The primary hypothesis regarding temperature maintenance is that at least 75% of the subjects' core temperatures remain between 36°C and 37.5°C for 80% of the steady state² time following the initial achievement of 37.5°C.

Outcomes	
Performance Outcomes
 
 1) This feasibility study is intended to confirm that the COOLSTAT system can cool within expected performance parameters and can reach and maintain normothermic cooling therapy over the study period. Subjects are expected to reach normothermia (core temperature $< 37.5^{\circ}\text{C}$) within 4 hours of starting COOLSTAT cooling. Subject temperatures are expected to be maintained within a 1.5°C temperature band, between $36^{\circ}\text{C} - 37.5^{\circ}\text{C}$, for 80% of the steady state time following the initial achievement of 37.5°C.¹

¹ This recognizes that some subjects will have short periods of break-through fever over the course of the study.

² If a subject must be disconnected from the CoolStat device for transport from the NCCU to another unit (e.g., to radiology or angiography suite), they will be reconnected to the device at steady state if their core temperature

	
2) Data collected will help to confirm cooling models and the control system algorithm by examining subject cooling response as a function of air flow rate and properties of the air supplied to the subjects.
 
3) The study will demonstrate that the COOLSTAT System can perform in the clinical setting and identify possible human and equipment interface refinements.
 
Safety Outcomes
 
Safety will be assessed by the following:
 
 4) The incidence and severity of all adverse events (including, but not limited to serious adverse events and non-related adverse events). 5) Assessment as to any potential contribution to the adverse event that may be device related or related to transnasal cooling therapy. 
Secondary Outcomes
 
This study may provide insight into the incidence of shivering, although the study design is not sufficiently powered to expect definitive conclusions.

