6.4 Safety Outcomes

An important outcome of this study is to assess the safety of high flow rate transnasal air delivery by the COOLSTAT device. The device safety will be addressed by the following:

³ This recognizes that some subjects will have short periods of break-through fever over the course of the study.

- The incidence and severity of all adverse events (including non-device-related adverse events) and the potential contribution to the adverse event that may be device related.
- Assessment by the investigator or their designee and attending physician(s) as to any adverse event that may be related directly to transnasal cooling.
- Confirmation based on a visual exam of the turbinates and upper airway that no clinically significant abnormal findings were attributable to transnasal air flow or the COOLSTAT device.

This study should also demonstrate that the COOLSTAT system can perform in the clinical setting.

The study may provide insight into the incidence of shivering, although the study design is not sufficiently powered to expect definitive conclusions.

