9.6 Tasks during Cooling

Once the COOLSTAT cooling has commenced, data will be manually collected and recorded on the supplied Therapy and Observation Record (requirements are also listed in Section 12.7). Data collection activities will be performed throughout the therapy phase (Phase 1.) These activities will include:

- Note the time when collecting data during this time interval.
- Note and record blood pressure and ICP values, prior to starting COOLSTAT, as well as during its use and after it is turned off.
- Record any antipyretic or other medications given and its dose during this time interval.
- Record the subject's core and tympanic temperatures displayed on the CoolStat and hospital monitor.
- Assess and record the subjects' level of shivering according to the Bedside Shivering Assessment Scale (scale written on the Data Record).
- Record any anti-shivering actions taken during this time interval.
- Check that the nasal mask has not inadvertently shifted during the study, and readjust if necessary during Phase 1. Apply a small amount of Vaseline to nasal

pillows to facilitate a good seal to nostrils without needing to apply much pressure.

- Briefly remove the nasal mask every 4 hours to inspect for any sign of pressure ulcer. Reapply Vaseline to facilitate good seal between nasal pillows and nostrils.
- Check that the saline bag is periodically dripping to ensure it is supplying saline to the disposable set during Phase 1 and record.
 - If the saline bag is observed to have <500 mL of saline remaining, replace saline bag with 1L bag to ensure continuous availability of saline.
 - Note when a bag is replaced on the Data and Observation Record.
- Record the tracheal volumes of fluid collected in the canisters from the tracheal tube at COOLSTAT therapy initiation (Phase 0) and twice daily for the remainder of the study. Oral fluids should be suctioned into a third canister and should not be included in the fluid volume measurements.
- Record if there was any AE during this time interval (a separate AE form must be completed.)
- Per standard of care, verify correct positioning of the endotracheal tube and record (three times daily). Exam subject for abdominal distension and record every 8 hours.

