9.7 Anti-Shivering Regimen

Shivering during cooling increases oxygen consumption and generates heat that interferes with the cooling process. If the subject starts shivering, anti-shivering regimen will be performed following existing hospital routines. A shivering response due to the application of an active, external cooling system is not unexpected. Any anti-shivering protocol that is used will be documented in the subject's case forms. The subjects will be actively monitored for signs of shivering. The proactive use of prophylactic anti-shivering agents should not be used.

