12.7 Collection of Manual Data

Subject core and tympanic temperatures, blood pressure, intracranial pressure (when available), suctioned water volume, and level of shivering will be monitored and recorded in the Therapy and Observation Record throughout the therapy period. Data to be collected during the course of the study is detailed in Section 9.0.

Data collection will occur at a minimum 5 minute intervals for the first 30 minutes of cooling, 30 minute intervals during the first 8 hours, and then every 2 hours for the remaining 16 hours (if applicable). During Phase 2, data collection will occur at a minimum of 15 minute intervals. After Phase 2, manual data will continue to be collected at a minimum of every 4 hours for the next 22 hours.

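### Section 13.2 assesses shivering only through anti-shivering actions, a proxy mixed with site practice, and specifies no summary of the shivering-scale scores already recorded in Phase 1

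*Combined protocol and SAP*

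**What the plan says.** **The outcome.** The Outcomes row of section 1.0 lists one secondary outcome: "This study may provide insight into the incidence of shivering, although the study design is not sufficiently powered to expect definitive conclusions". Section 6.4 repeats it: "The study may provide insight into the incidence of shivering".

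**The planned analysis.** Section 13.2 addresses the device's effect on shivering in one sentence: "the incidence of anti-shivering actions will be assessed". It does not say whether the unit is subjects with any action or the number of actions.

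**The data.** Section 9.6 asks staff to record the "level of shivering according to the Bedside Shivering Assessment Scale" and, as a separate item, "Record any anti-shivering actions taken during this time interval". Section 12.7 confirms that the "level of shivering will be monitored and recorded in the Therapy and Observation Record throughout the therapy period". On timing it says "Data collection will occur at a minimum 5 minute intervals for the first 30 minutes of cooling, 30 minute intervals during the first 8 hours". Beyond hour 8 the spacing widens to 2 hours.

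**The treatment rule.** Section 9.7 says that if a subject shivers, the "anti-shivering regimen will be performed following existing hospital routines". Sections 5.2 and 9.2 likewise leave shivering management to each site's standard procedures. Section 6.7 allows up to four sites. Section 9.7 also rules out prophylactic anti-shivering agents.

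**The concern.** The outcome is whether subjects shiver. The planned analysis asks whether they were treated for it. The two agree only if every shivering subject is treated and no one else is, at every site. The plan sets no common score at which treatment starts, so sites with different habits could report different action rates for the same amount of shivering.

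The direct measurement is on the therapy record, but no cut-off, per-subject summary or denominator is given for it. At stake is whether the study can give a readable descriptive answer to its own secondary question. The protocol itself treats shivering as relevant: section 9.7 notes that it generates heat that works against cooling.

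**Working it through.** The documents give no figure for shivering, so there is nothing to reproduce. The check has three parts.

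**1. How much direct data is scheduled (from section 12.7)**

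- First 30 minutes, every 5 minutes: 30 / 5 = 6 scores.
- From 30 minutes to 8 hours, every 30 minutes: 450 / 30 = 15 scores.
- From 8 to 24 hours, every 2 hours: 16 / 2 = 8 scores.
- Total after the start: 6 + 15 = 21 over 8 hours, and 21 + 8 = 29 over 24 hours.
- Section 13.0 plans 10 subjects at 8 hours and 20 at 24 hours. If all complete: 10 × 21 + 20 × 29 = 210 + 580 = 790 scheduled scores.

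**2. What an action count can reveal**

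Let p be the true proportion who shiver, s the chance that shivering leads to a recorded action, and g the chance of an action without shivering. Then

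P(action) = p × s + (1 − p) × g.

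None of the three is in the documents. The values below are assumptions: s from 0.5 to 1.0 and g from 0 to 0.2.

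| True p | Lowest action rate (s = 0.5, g = 0) | Highest action rate (s = 1, g = 0.2) |
|---|---|---|
| 10% | 0.10 × 0.5 = 5% | 0.10 + 0.90 × 0.2 = 28% |
| 30% | 0.30 × 0.5 = 15% | 0.30 + 0.70 × 0.2 = 44% |
| 50% | 0.50 × 0.5 = 25% | 0.50 + 0.50 × 0.2 = 60% |

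Different truths can give the same result. An action rate of 30% fits p = 30% with s = 1 and g = 0, and also p = 50% with s = 0.5 and g = 0.1, since 0.25 + 0.05 = 0.30. If prophylaxis is avoided as section 9.7 asks, g should be near 0 and the error is mainly an undercount. Even then, p cannot be recovered without s.

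**3. Precision of a score-based summary**

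Section 13.0 bars merging the nostril groups, so the groups are 20 and 10. One subject is 1/20 = 5 points or 1/10 = 10 points. If 30% shiver (assumed), the exact (Clopper-Pearson) 90% confidence interval is 14% to 51% for 6/20 and 9% to 61% for 3/10. The better measure is therefore still only descriptive.

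**The case against.** **The actions do carry information about shivering.** A reader might infer that 13.2 measures site practice instead of shivering. The text does not support that. Section 9.7 ties treatment to the onset of shivering and excludes prophylaxis, so actions will track shivering, imperfectly.

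**There are other routes to the data.** A reader might also infer that untreated shivering is lost and the scores are never analysed. Shivering is an anticipated adverse event (section 10.4), and reported adverse events are tabulated (section 1.0). Section 13.0 has a general rule that categorical variables get percentages and confidence intervals, which could be read to cover the scores. Both points stand. However, the first depends on shivering being reported as an adverse event, and the second gives no cut-off or per-subject summary for up to 29 repeated scores.

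**Scores can miss episodes too.** After hour 8 they may be 2 hours apart, whereas actions are recorded for the whole interval. An episode treated and settled between two scores appears only as an action. This stands, and it is why neither measure should replace the other.

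**Comparison with surface cooling.** Section 5.5.1 expects less shivering than with surface cooling, and a reader might infer that the choice in 13.2 is what prevents the study from showing it. It is not: the study has no surface-cooled comparator, so no shivering measure could show it. The plan also disclaims definitive conclusions.

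**Conclusion.** The mismatch holds. The named outcome is the incidence of shivering, the only analysis specified for it is a treatment-based proxy, and the direct score recorded throughout Phase 1 has no specified summary. The proxy cannot identify incidence unless the chances of treatment with and without shivering are known and alike across sites, and the plan does not supply this.

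The size of any bias is unknown. The 15% to 44% range at a true 30% rests entirely on assumed treatment probabilities and shows only that the gap could be material. Severity is low: the outcome is secondary, single-arm and explicitly unpowered, and the primary analyses and sample size are unaffected.

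**What to change.** Amend section 13.2 to report the following descriptively, separately for the double and single nostril groups:

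- the proportion of subjects with any Phase 1 scale score at or above a cut-off fixed before analysis, with an exact 90% confidence interval (the level section 13.0 already uses);
- the distribution of the worst Phase 1 score per subject;
- side by side with these, the proportion of subjects with any anti-shivering action, with an exact interval, and also shown by site.

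The cut-off is for analysis only and does not touch how shivering is managed. The scale levels are not printed in the protocol, so the sponsor should set the cut-off from the version on the data record. Use a Phase 0 score as baseline only if the case report form collects one. Section 9.6 places scoring in Phase 1, and the Phase 0 items in section 1.0 do not clearly include it.

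Cost: a few lines in 13.2 and one table, from Phase 1 data already recorded. There are no added subjects or assessments. Label: free improvement.
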